4.16. Collection, reporting and management of AEs and SAEs

Adverse events will be tracked and rated as mild, moderate or severe by the patient and rated as related to NRT by the research assistant using guidelines. We will determine if any adverse events result in dropouts or are serious according to FDA guidelines (95, 96). A DSMB will assist in determining if the rate or severity of adverse events exceeds expectations (see Protection of Human Subjects).

The research staff will report any unexpected AEs or any scores of "severe" on the side-effect symptom rating form or any FDA-defined serious AEs to the PI within 24 hrs so that the PI can decide on the appropriate action. All unexpected AEs will be monitored while they are active to determine if treatment is needed. Since a maximum two week supply of OTC nicotine lozenge and patch will be provided, adverse events will be rare. Nonetheless, they will be coded on a weekly basis using the FDA's COSTART rules and entered into a database. For each weekly study meeting, the research assistants will prepare a summary of all AEs, including their severity, whether they occurred during smoking or abstinence, caused a dropout, required treatment and presumed relation to drug intake. The PI will review this at the weekly study meeting (or before if more urgent). At the weekly meeting (or before if urgent), research assistants will report any premonitory symptoms of emergence of a mental disorder such as depression or alcohol dependence. [name], a board-certified psychiatrist, will be available for on-site medical supervision.

4.17 Plans for Interim Analyses of efficacy data

We plan to examine the data halfway through enrollment to determine if observed differences in quit rates are so large that the trial should be stopped early. Using the method of O'Brien and Fleming (129) the significance level for this interim analysis is $\alpha = 0.005$. According to this same reference, conducting this analysis decreases our power for detecting our projected differences only from 0.80 to 0.79.

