4.2 Primary and secondary outcomes

The primary outcome on which our study is powered is 7-day point prevalence at 6 month follow-up, which, unlike continuous abstinence, allows for delayed quitting. Unlike traditional cessation trials, there is no uniform quit date for all participants in the current trial, and thus anchoring abstinence to a designated quit attempt is unrealistic. However, we will track a number of secondary outcomes, including 30-day point prevalence abstinence, and incidence, frequency, latency, and duration of quit attempts (both self-defined and those lasting >24hrs), as well as smoking reduction (% reaching 50% reduction between baseline and end-of-study), provider acceptability and cost-effectiveness.

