4.6 Projected Timetable

The timetable is as follows:

	Year 1 (months)	Year 2 (months)	Year 3 (months)	Year 4 (months)	Year 5 (months)
Refine all procedures	1-6				
Procure supplies	1-6				
Refine recruitment methods	1-6				
Hire and train Central Personnel	5-8				
Hire & Train Additional Personnel*		13	25	37	
Pre-trial Focus groups (n=4)	7-8				
Train Clinic Personnel		Rolling, as new sites come on line			
Study Enrollment					
Cumulative Clinics to Begin Enrollment**	(2)	(7)	(13)	(17)	(20)
Cumulative N to start*** ^a	(116)	(406)	(754)	(986)	(1300)
First Participant Starts	10				
First Participant Completes		16			
Last Participant Starts					50
Last Participant Completes					56
Data Analysis					56-60
Manuscript Preparation					56-60

* Additional study personnel beyond year one per budget justification; All numbers reflect months within total study duration (**with the exception of cumulative clinics to begin recruitment, and cumulative N); ^a assumes average of 58 participants recruited per clinic

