as the covariate, estimated using generalized estimating equations (GEE) to account for clustering within clinic. Rates for each outcome will be estimated along with its 95% confidence interval. The coefficient on group will be evaluated using a Wald test to determine if the abstinence rates in the two arms are statistically significantly different at the one-sided 0.025 level. Additional regression modeling will be performed where covariates such as age, gender, and race are accounted for. We will also consider interactions between NRT and categorical covariates to determine if there are certain subgroups in which NRT sampling is more or less effective. Though we expect few individuals to make more than one quit attempt over the span of 6 months, and thus examine incidence of quit attempts (Hypothesis 2), we will examine the distribution of quit attempts, and if appropriate, examine number of quit attempts via Poisson regression modeling. In addition to binary outcomes of treatment uptake (Hyp. 3), we will test for continuous outcomes (e.g., treatment intensity, duration) via GEE regressions.

Hypotheses 1b Hypothesis 1b predicts that provision of NRT samples will result in longer period of abstinence (longest # days non-smoking) across the entire study duration, and will be evaluated using regression modeling via GEE accounting for clustering by clinic.

Secondary Analyses

Provider Acceptability We will provide separate, descriptive data on provider acceptance and satisfaction with treatment delivery. We do not plan any formal between group comparisons because of very limited sample size (14 clinics in each site). This study is not powered on provider-level outcomes of our intervention, but such data will be useful as we consider expanding our intervention into different venues.

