4.13 Trial stopping rules

There are three potential reasons to stop the trial prematurely: a) undermining of cessation, b) higher-than-anticipated quit rates, and c) significant rate of adverse events. Each is addressed below.

a) To protect against undermining of cessation, we will form a Data Safety and Monitoring Board (DSMB) and have them conduct an interim analysis after 50% of the sample has completed 6 month follow-up. We chose this number as this is the minimum necessary given our base rate is projected to be 15% and one has to see clear trend toward an even lower rate. To do this, the statistician will provide a copy of the dataset to the board. If this occurs, this board will independently decide on whether to stop the study.

b) We plan to examine the data halfway through enrollment to determine if observed differences in quit rates are so large that the trial should be stopped early. Using the method of O'Brien and Fleming (129) the significance level for this interim analysis is $\alpha = 0.005$. According to this same reference, conducting this analysis decreases our power for detecting our projected differences only from 0.80 to 0.79.

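### The O'Brien-Fleming efficacy look is timed by enrolment, when about 37% of 6-month outcomes would be in, and the final test keeps the full one-sided 0.025 instead of the matching 0.0240

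*Combined protocol and SAP*

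**What the plan says.** Sections 4.13(b) and 4.17 plan one efficacy look by the O'Brien-Fleming method at a significance level of 0.005. Section 4.17 gives its timing and purpose: "We plan to examine the data halfway through enrollment to determine if observed differences in quit rates are so large" that an early stop is warranted. Section 4.13(b) likewise says to "examine the data halfway through enrollment". Neither section says whether 0.005 is one- or two-sided, gives a level for the final analysis, or ties the boundary to the amount of outcome data. Both state that "conducting this analysis decreases our power for detecting our projected differences only from 0.80 to 0.79".

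Section 4.9 tests the group coefficient from the GEE logistic model with a Wald test, to see whether the arms are "statistically significantly different at the one-sided 0.025 level". It does not mention the interim look.

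The endpoint is set in section 4.2: "The primary outcome on which our study is powered is 7-day point prevalence at 6 month follow-up". By contrast, the harm look in section 4.13(a) is tied to outcomes: the board is to "conduct an interim analysis after 50% of the sample has completed 6 month follow-up".

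**The concern.** An O'Brien-Fleming boundary is a function of the information available at the look. With an outcome that takes 6 months to observe, half of enrolment is not half of the information. A level computed for the halfway information point is too easy to cross if it is applied earlier. Early caution is the reason for choosing this boundary.

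The method also fixes two levels, one for the look and one for the end. The plan states the first and leaves the final test at the full 0.025, so the two tests together spend more than 0.025.

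At stake are an efficacy stop resting on about a third of the outcomes, and an overall type I error slightly above the level claimed.

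**Working it through.** **Inputs.** Total N 1300 (4.4). Cumulative accrual 116, 406, 754, 986, 1300 over Years 1 to 5 (4.6, row "Cumulative N to start"), read as year-end totals. Follow-up 6 months (4.2). Interim level 0.005 and power 0.80 falling to 0.79 (4.17). Final level one-sided 0.025 (4.9).

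**Model.** The interim and final statistics are bivariate normal with correlation √t, where t is the information fraction, counted here in participants. The two-look O'Brien-Fleming boundary is c/√t at the look and c at the end, with c chosen so that the overall one-sided error is 0.025.

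**1. The plan's own figures.** At t = 0.5, c = 1.9774.
- Look: z = 1.9774/√0.5 = 2.797, p = 0.0026 one-sided or 0.0052 two-sided.
- End: z = 1.977, p = 0.0240 one-sided.

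The stated 0.005 is therefore reproduced as a two-sided level at half information. As a check on the other reading, an overall one-sided level of 0.05 would give an interim one-sided level of 0.0088, which does not match.

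For power, the drift that gives 0.80 with no look is 1.960 + 0.842 = 2.802.
- Final level 0.0240: power 0.797, close to the stated 0.79.
- Final level 0.025 kept: power 0.802, so no loss.

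The stated fall thus assumes a reduced final level that section 4.9 does not contain.

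**2. Outcomes available at half enrolment.** Interpolating linearly within Year 3:
- Participant 650 enrols at month 24 + 12 × (650 − 406)/(754 − 406) = 32.4.
- Those with 6-month outcomes enrolled by month 26.4: 406 + 348 × 2.41/12 = 476, and 476/1300 = 36.6%.

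Other assumptions give somewhat less. Uniform accrual over months 10 to 50 gives (24 − 10)/40 = 35% (455 participants). A look at the calendar midpoint, month 30, gives 406/1300 = 31%.

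**3. Boundary at that point.** Solving the same shape at t = 0.366 gives c = 1.964, so the look is at z = 1.964/√0.366 = 3.25, p = 0.0012 two-sided. The nominal level 0.005 is larger by 0.005/0.00117, about 4.3 times.

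**4. Overall one-sided error with the final test at 0.025.**

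| Reading of 0.005 | Interim z | t = 0.50 | t = 0.366 |
|---|---|---|---|
| Two-sided | 2.807 | 0.0259 | 0.0264 |
| One-sided | 2.576 | 0.0273 | 0.0280 |

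The final level that would hold 0.025 is 0.0240 (t = 0.50) or 0.0236 (t = 0.366) on the two-sided reading. On the one-sided reading it is 0.0226 or about 0.0219.

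**5. Chance of stopping at the look, at drift 2.802.** The mean of the interim statistic is 2.802√t, which is 1.695 at t = 0.366 and 1.981 at t = 0.50.
- As written, two-sided reading, t = 0.366: P(Z > 2.807 − 1.695) = 13%.
- Matching boundary, t = 0.366: P(Z > 3.246 − 1.695) = 6%.
- Look moved to t = 0.50: P(Z > 2.797 − 1.981) = 21%.

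**The case against.** The strongest objection is that the error consequence is slight. On the two-sided reading, the early trigger adds only about 0.0004 (0.0264 − 0.0259) and the unadjusted final level about 0.0009 (0.0259 − 0.0250). The factor of four compares two small nominal p-values and is not an inflation of the error rate. This is right, and it limits the severity of the point. It does not remove it: 0.025 is exceeded under every reading, and the chance of a premature stop roughly doubles.

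The wording may also be loose. The cited method, the level 0.005 and the stated power loss all fit a look at half information, and 0.025 may have been meant as the overall level. That may well be the intention. But section 4.13 places an outcome-based trigger in (a) directly beside an enrolment-based trigger in (b), and section 4.9 applies 0.025 to the Wald test itself. A reader following the text would carry out the wrong rule.

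Three limits stand:
- The 37% is an interpolation of projected accrual. The timetable is itself uneven: its footnote of 58 per clinic gives 20 × 58 = 1160, not 1300.
- Participants stand in for information. With randomization by clinic, the true fraction also depends on the intraclass correlation, which the supplied text does not give. At 58 per clinic, the early look would rest on about 476/58 ≈ 8 clinics and a look at 650 on about 11. Normal theory for a clustered Wald test is then itself approximate.
- The sample-size rationale is referred to section C.10 of the grant, which was not available. The statement that no reduced final level is given covers the supplied text only.

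**Conclusion.** The concern holds. As written, the rules do not deliver the O'Brien-Fleming design they cite. The look would fall when roughly 31% to 37% of outcomes are in (37% on the tabled accrual) and would use a level that fits only 50%. The final test is not reduced to the matching 0.0240. Overall one-sided error is 0.0259 to 0.0264, or up to 0.0280 if 0.005 is one-sided. The missing sidedness is an omission and not a conflict, because the two-sided reading pairs correctly with one-sided 0.025. The type I excess is minor; the looser early-stop boundary is the larger of the two faults. The point should be fixed, but it does not threaten the trial. The figures assume normal theory, information proportional to participants, and linear accrual within years.

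**What to change.** - **Sections 4.13(b) and 4.17:** hold the efficacy look when 650 participants have reached 6-month follow-up, on the same data cut as the harm look in 4.13(a). State the threshold as one-sided p < 0.0026 (z 2.797).
- **Section 4.9:** test the primary outcome at the end at one-sided p < 0.0240 (z 1.977), and state that 0.025 is the overall level.
- **Alternative:** Lan-DeMets spending of O'Brien-Fleming type at the actual information fraction. This is a different rule: at half information it spends about one-sided 0.0015 at the look, with the final level solved to match. It suits the uncertainty about the fraction. One of the two should be chosen and written down.

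The cost is wording only. Power falls from 0.800 to 0.797, within the fall to 0.79 already stated. The look moves about 6 months later, to month 32.4 + 6 = 38.4. About 754 + 232 × 2.41/12 ≈ 800 would then be enrolled, so an early stop could still spare about 500 of the 1300.

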4.18 Responsibility for data and safety monitoring

The PI will be responsible for monitoring the trial. The statistician will monthly examine the outcomes database for missing data, unexpected distributions or responses, and outliers. The PI will weekly check the AE database prepared by the research assistants immediately prior to the lab meeting a) to see if any particular COSTART categories are being endorsed more frequently than normal and b) to determine if any side-effect symptom checklist scores are higher than expected. A DSM report will be filed with the IRB and funding agency on a yearly basis, unless greater than expected problems occur. The report will include participant characteristics, retention and disposition of study participants, quality assurance issues and reports of AEs, significant/unexpected AEs and serious AEs. We will report efficacy at the end of the trial.

4.19 Frequency of DSM reviews

The DSMP will be reviewed annually.

4.20 Content of DSM report

The DSM report, which will be provided to all DSMB members, will include: a) enrollment data, in aggregate and split by gender and race, b) retention (% of all scheduled contacts that are completed), and c) adverse event data. Adverse event data will be presented in aggregate, but will also include a detailed listing of all serious adverse events (SAEs).

